PRO	Patient Reported Outcome
Q2W	Every 2 weeks
RA	Rheumatoid Arthritis
RF	Rheumatoid Factor
SAE	Serious adverse event
SAP	Statistical analysis plan
SAS	Statistical Analysis Software
sCD40L	Soluble CD40 ligand
SD	Standard Deviation
SJC	Swollen Joint Count
SPP	Statistical Programming Plan
TJC	Tender Joint Count
Anti-TNFa	Anti-Tumour Necrosis Factor alpha
VAS	Visual Analogue Score

1 INTRODUCTION

This document describes the statistical analyses for protocol D5100C00002, a multicenter, randomized, double-blind, placebo-controlled study to evaluate the safety and tolerability of multiple ascending doses of MEDI4920 in subjects with adult-onset rheumatoid arthritis (RA) (moderate to severe, as defined by disease activity score in 28 joints using C-reactive protein (DAS28 CRP) \geq 3.2 at screening) with an inadequate response to methotrexate (MTX) or other conventional disease-modifying anti-rheumatic drugs (cDMARDs) or a biologic anti-tumor necrosis factor alpha (anti-TNF α) agent.

A separate statistical programming plan (SPP) will contain the table templates, detailed specifications and programming code for the statistical analyses.

2 STUDY OVERVIEW

2.1 Study Objectives

2.1.1 Primary Study Objective

To assess the safety and tolerability of multiple ascending intravenous (IV) doses of MEDI4920 in subjects with adult-onset RA.

2.1.2 Secondary Study Objectives

To evaluate the pharmacokinetics (PK) and immunogenicity of MEDI4920 in subjects with adult-onset RA.

2.1.3 Exploratory Study Objectives

2.2 Study Design

This is a multicenter, randomized, double-blind (investigator, subject, and sponsor will be blinded to treatment assignment), placebo-controlled study to evaluate the safety and tolerability of multiple ascending doses (MADs) of MEDI4920 in subjects with adult-onset RA (moderate to severe, as defined by DAS28 CRP \ge 3.2 at screening) with an inadequate response to MTX or other cDMARDs or a biologic anti-TNF α agent.

Approximately 40 subjects on stable MTX or another cDMARD will be randomized across 3 cohorts to receive either 75 mg (Cohort 1), 500 mg (Cohort 2), or 1500 mg (Cohort 3) MEDI4920, or placebo once every 2 weeks (Q2W).

An additional 14 subjects may be randomized to an additional cohort (Cohort 4) if required, to understand the dose (exposure) - response relationship. The selected dose and exposure (maximum concentration (C_{max}) and area under the concentration-time curve (AUC)) will not be higher than 1500 mg Q2W and could include a less frequent dosing regimen (eg, once every 4 weeks).

Subjects will undergo a screening period of up to 6 weeks followed by randomization and treatment for 12 weeks. Subjects will be followed for an additional 12 weeks after the treatment period for safety.

Subjects will receive an IV dose of MEDI4920 or placebo Q2W for up to 12 weeks as follows:

- Cohort 1: 75 mg MEDI4920 (N = 8) or placebo (N = 2) as a single IV dose administered over at least 30 minutes Q2W
- Cohort 2: 500 mg MEDI4920 (N = 10) or placebo (N = 4) as a single IV dose administered over at least 60 minutes Q2W
- Cohort 3: 1500 mg MEDI4920 (N = 12) or placebo (N = 4) as a single IV dose administered over at least 90 minutes Q2W
- Cohort 4 (Optional): MEDI4920 (N = 10) or placebo (N = 4) as a single IV dose (duration of infusion and frequency of administration to be determined)

All subjects will receive a total of 7 doses of investigational product (MEDI4920 or placebo) during the 12-week treatment period.

The primary analysis will be performed when all subjects in Cohort 3 have completed the Day 85 assessments or have been withdrawn from the study. The primary analysis will include all assessments on the subjects prior to the data cut-off for the primary analysis.

If a fourth cohort is required, the data will be analyzed when all subjects in the fourth cohort have completed the Day 85 assessments or have been withdrawn from the study.

The final analysis on the subjects will be performed when all subjects have completed the safety follow-up.

2.3 Treatment Assignment and Blinding

An interactive voice/web response system (IXRS) will be used for randomization to a treatment group and assignment of investigational product kit numbers if assigned to an active treatment arm. A subject is considered randomized into the study when the investigator notifies the IXRS that the subject meets eligibility criteria and the IXRS provides the assignment of treatment group and allocates active treatment if assigned to the active treatment arm.

Subjects will be randomized in a 4:1 ratio (Cohort 1), in a 5:2 ratio (Cohort 2), in a 3:1 ratio (Cohort 3), and in a 5:2 ratio (Optional Cohort 4) to receive either MEDI4920 or placebo respectively.

This is a double-blind study in which MEDI4920 and the saline placebo are not identical in appearance. For maintaining the blinding of the principal investigator, site staff, sponsor, Contract Research Organization (CRO) or staff, a local unblinded pharmacy staff member will be nominated by each site and will have the responsibility of allocating, dispensing and preparing the investigational product in order to maintain the study blind. In addition, a separate unblinded monitor will be used for the oversight of investigational product management.

MedImmune personnel will be unblinded to the subject treatment assignments at the primary analysis (Day 85). The data from the primary analysis will not be communicated to personnel at the CRO or investigational sites or to enrolled subjects, until the study is complete.

2.4 Sample Size

No formal sample size calculations are presented for the evaluation of the primary objective of safety and tolerability of MEDI4920. The sample size calculations are based on the exploratory endpoint CC

CCI .

CCI

The sample size calculation for the change from baseline in DAS28 CRP at Week 12 is based on combining the data from the cohorts and performing a dose response analysis. Based on the assumption **CC**

, the sample sizes of 10,

8, 10 and 12 subjects for the placebo, 75, 500 and 1500 mg dose groups, respectively, will

provide approximately 80% power for detecting a statistically significant dose response, using a significance level of 0.10.

The power for dose response has been calculated using a multiple comparison procedure with modeling techniques (MCP-Mod; Bretz et al, 2005), with three candidate models for the dose response (linear, maximum effect attributable to the drug $[E_{max}]$, and a Hill- E_{max} model). An overall significance level of 0.10 will be used to test for dose response.

3 STATISTICAL METHODS

3.1 General Considerations

All data will be provided in data listings sorted by treatment group and subject number. Tabular summaries will be presented by treatment group. Categorical data will be summarized by the number and percentage of subjects falling within each category. In general, continuous variables will be summarized by descriptive statistics including mean, standard error or standard deviation (SD), median, minimum, and maximum.

Day 1 will be defined as the day of first investigational product administration. Baseline will be defined as the last non-missing value prior to the first administration of investigation product. The change from baseline will be calculated by subtracting the baseline values from the individual post-baseline values. If either the baseline or post-baseline value is missing, the change from baseline is set to missing.

Unless otherwise stated, all efficacy analyses will be conducted with a two-sided test at a significance level of $\alpha = 0.10$.

Data analyses will be conducted using the SAS[®] System Version 9.3 or higher (SAS Institute Inc., Cary, NC) in a UNIX platform.

3.1.1 Visit windows

Visit windows will be used for all scheduled assessments to allow for by-visit analyses, since not all assessments are performed on the scheduled day. Unless specified otherwise, all efficacy and safety analyses will be based on the analysis visit windows. The actual assessment day will be mapped to the planned study visit following the analysis visit windowing rules below:

• If more than one assessment falls within a visit window, the closest non-missing assessment to the scheduled day will be used in the analysis.

• If two non-missing assessment actual dates are equidistant from the target day, the earlier visit will be used in the analysis.

The visit windows will be calculated by bisecting the scheduled visit days. The lower limit of each window will be the mean of the two adjacent planned study days, rounded up to the nearest integer, except for the first post-treatment visit, which will start at 2. The upper limit of each window will be the mean of the two adjacent planned study days, rounded down to the nearest integer.

Table 3.1.1-1Visit windows for DAS28, CDAI, Joint Counts, Patient
Global Assessment, Physician Global Assessment, CRP
and ESR

Planned study day of visit	Visit window	
1	All assessments prior to the first administration of investigation product	
15	Start of first administration of investigation product – Day 22	
29	Day 23 - 43	
57	Day 44 - 71	
85	Day 72 - 99	
113	Day 100 - 127	
141	Day 128 - 155	
169	Day 156 +	

Table 3.1.1-2 Visit windows for Vectra DA

Planned study day of visit	Visit window	
1	All assessments prior to the first administration of investigation product	
15	Start of first administration of investigation product – Day 22	
29	Day 23 - 43	
57	Day 44 - 71	
85	Day 72 - 99	
113	Day 100 - 141	
169	Day 142 +	

Table 3.1.1-3Visit windows for laboratory assessments

Planned study day of visit	Visit window	
1	All assessments prior to the first administration of investigation product	
8	Start of first administration of investigation product – Day 11	
15	Day 12 - 22	
29	Day 23 - 43	
57	Day 44 - 71	
85	Day 72 - 88	

Planned study day of visit	Visit window
92	Day 89 - 95
99	Day 96 - 106
113	Day 107 - 127
141	Day 128 - 155
169	Day 156 +

Table 3.1.1-3Visit windows for laboratory assessments

Table 3.1.1-4Visit windows for ECGs

Planned study day of visit	Visit window	
1	All assessments prior to the first administration of investigation product	
85	Start of first administration of investigation product – Day 127	
169	Day 128 +	

Vital signs will be summarized according to the eCRF recorded assessment visit.

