2.1.3 Exploratory Objectives

2.2 Study Endpoints

2.2.1 **Primary Endpoints**

- 1. The incidence of AEs and SAEs.
- 2. The incidence of treatment-emergent AEs of special interest (AESIs) as follows:
 - Thrombotic and embolic events
 - Hepatic function abnormality (meeting the definition of Hy's Law [HL]; see Section 5.6.2)
 - Anaphylaxis and serious hypersensitivity reactions
 - Infusion-related reactions

- Immune complex disease
- Serious and/or opportunistic infections (including but not limited to reactivation of latent viral infection [varicella zoster (VZ), herpes simplex virus (HSV), EBV, CMV] and TB)
- 3. Vital signs, laboratory parameters (including coagulation parameters), electrocardiograms (ECGs), and physical examinations.

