4.2.2 Treatment Period

Table 4.2.2-1 shows all procedures to be conducted during the treatment period (Part A through Day 85 [Week 12]).

Whenever vital signs, 12-lead ECGs, and blood draws are scheduled for the same nominal time, blood draws should occur last. The timing of the first two assessments should be such that it allows the blood draw (eg, PK blood sample) to occur at the proper nominal time. All laboratory sample collections and assessments on dosing day must be performed at predose, unless specified otherwise.

Study Period	Treatment Period								
Visit Number	V2	V3	V4	V5	V6	V7	V8	V9	V10
Procedure / Study Day	Day 1 ± 1 Day	Day 2 ± 1 Days	Day 8 ± 1 Day	Day 15 ± 1 Day	Day 29 ± 1 Day	Day 43 ± 1 Day	Day 57 ± 1 Day	Day 71 ± 1 Day	Day 85 ± 1 Day
Randomization						-			
Verify eligibility criteria	Х								
IXRS randomization call	Х								
Safety assessments									
Assessment of AEs/SAEs	Х	Х	Х	Х	Х	Х	Х	Х	Х
Assessment of concomitant medications	Х	Х	Х	Х	Х	Х	Х	Х	Х
Complete physical examination (includes weight)	Х								
Abbreviated physical examination ^a			Х	Х	Х	Х	Х	Х	Х
12-lead ECG	Х								Х
Vital signs ^b	Х	Х	Х	Х	Х	Х	Х	Х	Х
Blood collection for:									
Serum chemistry	Х		Х	Х	Х		Х		Х
Hematology	Х		Х	Х	Х		Х		Х
Coagulation panel	Х		Х	Х	Х		Х		Х
Autoantibody panel (RF, RF isotypes, ACPA, ANA, anti-Ro, anti-La [serum])	Х				Х		Х		Х
Exploratory biomarkers (serum)	Х		Х	Х	Х		Х		Х
RNA PAXgene (whole blood)	Х			Х	Х		Х		Х
Acute-phase reactants (CRP, ESR ^c)	Х			Х	Х		Х		Х
CD4+ counts	Х		Х	Х		Х	Х	Х	Х
Flow cytometry (whole blood)	Х				Х		Х		Х
Vectra® DA (MBDA) (serum)	Х		Х	Х	Х		Х		Х
Total CD40L (plasma)	Х		Х	Х	Х		Х		Х
PK (plasma)	X d	Х	Х	X e	X e		X e		X e
ADA (plasma) ^f	Х				Х		Х		Х
Anti-PAD4 antibody (serum)	Х				Х		Х		Х
Urine collection for:		•		-	-		-	-	
Urinalysis	Х		Х			Х	Х	Х	Х

Table 4.2.2-1 Schedule of Treatment Period Study Procedures

Study Period	Treatment Period								
Visit Number	V2	V3	V4	V5	V6	V7	V8	V9	V10
Procedure / Study Day	Day 1 ± 1 Day	Day 2 ± 1 Days	Day 8 ± 1 Day	Day 15 ± 1 Day	Day 29 ± 1 Day	Day 43 ± 1 Day	Day 57 ± 1 Day	Day 71 ± 1 Day	Day 85 ± 1 Day
Urine β -hCG (women of childbearing potential only)	Х			Х	Х	Х	Х	Х	Х
Rheumatoid assessments									
TJC/SJC: 28 joints count	Х			Х	Х		Х		Х
VAS Patient assessment of disease activity	Х			Х	Х		Х		Х
Physician's global assessment	Х			Х	Х		Х		Х
Investigational product administration	X			X	X	X	X	X	X

Table 4.2.2-1 Schedule of Treatment Period Study Procedures

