3.7.4 Clinical Laboratory Evaluation

Serum chemistry, hematology, coagulation and urinalysis parameters will be collected in this study, analyzed by central laboratory and will be used to investigate the safety of MED4920.

For continuous variables of laboratory tests, all data at baseline and at each scheduled visit will be summarized by treatment group using descriptive statistics. Changes from baseline to each scheduled time point of post-dose will also be summarized using descriptive statistics. For categorical variables of laboratory tests, the frequency and percentage in each category of the item at baseline and at each scheduled visit of post-dose will be presented for each treatment group.

Boxplots of each laboratory variable by study visit will be presented for each treatment group. The boxplots will contain all the data. The boxes will extend to the limits of the interquartile range and the whiskers will extend to the most extreme observation within 1.5 times the interquartile range from the nearest quartile. The data will be plotted on a logarithmic scale when it improves interpretability of the plot. Reference lines will be included on the boxplots for the limits of the normal range.

Laboratory results will also be summarized by Common Terminology Criteria for Adverse Events (CTCAE) grade by visit for the parameters included in Table 3.7.4-1.

Lab parameter	Toxicity grade	Lab values
White blood cell count $(10^9/L)$	Grade 0	\geq LLN
	Grade 1	\geq 3 - <lln< td=""></lln<>
	Grade 2	$\geq 2 - <3$
	Grade 3	$\geq 1 - <2$
	Grade 4	<1
Platelets (10 ⁹ /L)	Grade 0	\geq LLN
	Grade 1	≥ 75 - <lln< td=""></lln<>
	Grade 2	≥ 50 - <75
	Grade 3	\geq 25 - <50

Table 3.7.4-1 CTC grades

Lab parameter	Toxicity grade	Lab values
•	Grade 4	<25
Lymphocytes (10^9/L)	Grade 0	≥LLN
	Grade 1	≥ 0.8 - <lln< td=""></lln<>
	Grade 2	≥ 0.5 - <0.8
	Grade 3	≥ 0.2 - <0.5
	Grade 4	<0.2
Neutrophils (10^9/L)	Grade 0	≥LLN
	Grade 1	≥ 1.5 - <lln< td=""></lln<>
	Grade 2	≥ 1.0 - <1.5
	Grade 3	≥ 0.5 - <1.0
	Grade 4	<0.5
ALT (IU/L)	Grade 0	≤ULN
	Grade 1	> ULN - ≤3*ULN
	Grade 2	> 3*ULN - ≤5*ULN
	Grade 3	> 5*ULN - <20*ULN
	Grade 4	>20*ULN
AST (IU/L)	Grade 0	≤ULN
	Grade 1	> ULN - ≤3*ULN
	Grade 2	> 3*ULN - ≤5*ULN
	Grade 3	> 5*ULN - <20*ULN
	Grade 4	>20*ULN
Bilirubin (umol/L)	Grade 0	≤ULN
	Grade 1	> ULN - ≤1.5*ULN
	Grade 2	> 1.5*ULN - ≤3*ULN
	Grade 3	> 3*ULN - <10*ULN
	Grade 4	>10*ULN

Table 3.7.4-1CTC grades

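### The SAP's single laboratory window table does not fit the urinalysis schedule: on-time Day 43 results are tabulated as Day 29, and Day 71 results normally drop out of the by-visit tables

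*SAP*

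**What the plan says.** SAP 3.1.1 sets the scope of windowing: "Unless specified otherwise, all efficacy and safety analyses will be based on the analysis visit windows". Windows are built from the planned days: "The visit windows will be calculated by bisecting the scheduled visit days". When several results share a window, only one is kept: "If more than one assessment falls within a visit window, the closest non-missing assessment to the scheduled day will be used in the analysis". Table 3.1.1-3 is the only window table for laboratory data. The one stated exemption is: "Vital signs will be summarized according to the eCRF recorded assessment visit".

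SAP 3.7.4 places urinalysis within the laboratory data: "Serum chemistry, hematology, coagulation and urinalysis parameters will be collected in this study, analyzed by central laboratory". For categorical items it plans that the "frequency and percentage in each category of the item at baseline and at each scheduled visit of post-dose will be presented".

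Protocol Tables 4.2.2-1 and 4.2.3-1 schedule post-dose urinalysis on Days 8, 43, 57, 71, 85, 99, 113, 141 and 169. Chemistry, hematology and coagulation are scheduled on Days 8, 15, 29, 57, 85, 92, 99, 113, 141 and 169.

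**The concern.** A window table works only if its planned days are the days on which the test is done. Table 3.1.1-3 carries the blood-test days, so urinalysis is sorted into visits at which it was not taken and has no row for two visits at which it was.

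Laboratory data belong to the third primary endpoint: "Vital signs, laboratory parameters (including coagulation parameters), electrocardiograms (ECGs), and physical examinations". The label also carries exposure information. Protocol 4.2.2 requires that "laboratory sample collections and assessments on dosing day must be performed at predose, unless specified otherwise", so a Day 43 urinalysis follows three doses (Days 1, 15 and 29). Shown as Day 29, it reads as following two (Days 1 and 15). In a multiple-dose safety study, that misstates how much drug preceded a finding. The urinalysis panel in Protocol 4.3.2 includes protein, blood and microscopy, and Protocol 1.6 names nephritis as a possible manifestation of immune complex disease, so the timing of these results is of some interest.

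**Working it through.** **Inputs.** Planned days and visit tolerances come from Protocol Tables 4.2.2-1 (±1 day) and 4.2.3-1 (±3 days). Window limits come from SAP Table 3.1.1-3.

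**1. Reproduce the SAP table.** The boundary between adjacent visits is (d1 + d2)/2. The earlier window ends at the boundary rounded down, and the later one starts the next day. For the blood-test days:

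| Pair | Midpoint | Earlier window ends |
|---|---|---|
| 8, 15 | 11.5 | 11 |
| 15, 29 | 22 | 22 |
| 29, 57 | 43 | 43 |
| 57, 85 | 71 | 71 |
| 85, 92 | 88.5 | 88 |
| 92, 99 | 95.5 | 95 |
| 99, 113 | 106 | 106 |
| 113, 141 | 127 | 127 |
| 141, 169 | 155 | 155 |

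This reproduces all ten post-baseline rows. The table is therefore the blood-test calendar, correctly tabulated for those tests.

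**2. Map urinalysis to that table.**

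| Urinalysis visit | Permitted days | Window(s) reached |
|---|---|---|
| 8 | 7–9 | 8 |
| 43 | 42, 43 | **29** |
| 43 | 44 | **57** |
| 57 | 56–58 | 57 |
| 71 | 70, 71 | **57** |
| 71 | 72 | **85** |
| 85 | 84–86 | 85 |
| 99 | 96–102 | 99 |
| 113 | 110–116 | 113 |
| 141 | 138–144 | 141 |
| 169 | 166–172 | 169 |

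Seven of nine visits reach their own row on every permitted day; Days 43 and 71 never do. Three of the ten rows (Days 15, 29 and 92) have no scheduled urinalysis.

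**3. Apply the closest-to-target rule.**
- Day 42 or 43: no urinalysis is scheduled on Day 29, so this sample becomes the Day 29 result.
- Day 44: |44 − 57| = 13 days, against 0–1 for the Day 57 visit's own sample. It is omitted.
- Day 70 or 71: |70 − 57| = 13 and |71 − 57| = 14, against 0–1. It is omitted.
- Day 72: |72 − 85| = 13, against 0–1. It is omitted.

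All 3⁴ = 81 combinations of −1, 0 and +1 day on Days 43, 57, 71 and 85 were run with every sample present. The Day 43 visit was relabelled Day 29 when taken on Day 42 or 43 and omitted when taken on Day 44. The Day 71 visit was omitted in all 81.

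**4. If a neighbouring sample is missing.** Without the Day 57 sample, a Day 44 sample is shown as Day 57 or, failing that, a Day 70 or 71 sample is. Without the Day 85 sample, a Day 72 sample is shown as Day 85.

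**5. Bisect the urinalysis days instead.** The midpoints are (8+43)/2 = 25.5, (43+57)/2 = 50, (57+71)/2 = 64, (71+85)/2 = 78, (85+99)/2 = 92, (99+113)/2 = 106, (113+141)/2 = 127 and (141+169)/2 = 155. All nine visits then map to their own row on every permitted day.

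**The case against.** The strongest counter-argument is that little depends on this. The tables are descriptive, all arms are handled alike, urinalysis is not among the CTCAE-graded parameters, AESIs are identified from adverse event review, and every value stays in the listings. SAP 3.7.4 also says the boxplots hold all the data, although categorical urinalysis results do not lend themselves to boxplots. All of this stands and limits the weight of the point.

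SAP section 1 leaves detailed specifications to a separate programming plan, which might handle urinalysis differently. That plan is not available here, and it would not correct an SAP that states a general rule with one exemption.

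The written rounding rule is also looser than the table. When a midpoint is a whole number, rounding up and rounding down give the same day, so the text puts that day in both windows, whereas the table gives it to the earlier visit. Days 43 and 71 are such midpoints. This does not rescue them: neither has a row, so any tie rule sends them to another visit.

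Finally, an early discontinuation visit or a repeat sample could also fall in Days 23–43, so the Day 29 row is filled from the Day 43 visit only as far as scheduled sampling goes. This is a small qualification.

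**Conclusion.** The concern holds. As written, the SAP mislabels or omits urinalysis from two of nine scheduled post-dose visits in the by-visit summaries. With the planned maximum of 54 subjects and full attendance, the ceilings are 54 Day 43 samples relabelled or omitted and 54 Day 71 samples omitted. These are upper bounds, not expected counts. Omission of Day 71 assumes that the Day 57 and Day 85 samples exist; otherwise the result can appear under the wrong visit.

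Chemistry, hematology and coagulation map correctly, and no inferential result or safety alert is affected. The SAP should be corrected because part of a primary safety endpoint would be tabulated at the wrong time point and the remedy is nearly free.

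Two side points need clarification only:
- CD4+ counts are also drawn on Days 43 and 71 and not on Day 29. They would be affected in the same way if tabulated under Table 3.1.1-3, but SAP 3.7.4 does not list them.
- Vectra DA is drawn on Day 8, but Table 3.1.1-2 has no Day 8 row, so a Day 8 value would stand in for a missing Day 15 value. This may be deliberate alignment with the DAS28 visits; the model specification is redacted.

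**What to change.** Add a urinalysis window table to SAP 3.1.1:

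| Planned day | Window |
|---|---|
| 8 | First dose to Day 25 |
| 43 | 26–50 |
| 57 | 51–64 |
| 71 | 65–78 |
| 85 | 79–92 |
| 99 | 93–106 |
| 113 | 107–127 |
| 141 | 128–155 |
| 169 | 156 onward |

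State that a whole-number midpoint belongs to the earlier visit, as the existing tables already assume. Alternatively, extend the vital-signs sentence so that urinalysis is also summarized by eCRF visit. If CD4+ counts are to be tabulated by visit, give them windows from their own schedule.

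For Vectra DA, either add a Day 8 row (first dose to Day 11) and set Day 15 to 12–22, or state that Day 8 is deliberately left out and exclude those samples from the Day 15 window.

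The cost is one small table or one sentence, plus one clarification. No new data or outputs are needed.
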